10.14. Appendix 14: Protocol Amendment History

This is an original protocol.

**AMENDMENT HISTORY**

SECTION(S)	CHANGE and RATIONALE
Global Change	“Pulse Pressure Product” and “Rate Pressure Product” were used interchangeably; the term “Rate Pressure Product” will be used going forward.
Abbreviations	Added abbreviation of ANCOVA, AHA and ATC. Remove abbreviations that are not in the body of the text. Minor corrections were made for AE(s), PRO, and PROMIS SF 10a.
1	Change the Clinical Protocol JNJ-64565111OBE2002 date to 5 April 2018.
2.1	Visit windows now include post-Week 12 to account for subjects brought back for visits to reduce Lost To Follow Ups.
2.2	Remove Section 2.2 Pooling Algorithm for Analysis Centers
2.2.2	Refined mITT Analysis Set definition to include subjects taking at least one dose of study medication.
2.2.2	Clarify that the Completers’ Analysis Set is defined by the Treatment Disposition eCRF status.
2.3	Remove Region because this study is conducted in the US only. Remove Ethnicity, Baseline fasting HOMA-B, and Baseline eGFR to reduce the number of subgroup analyses. A minor correction for the baseline HbA 1c categories was made.
2.3, 4.1	Correct variable name for HOMA-B and HOMA-IR.
4.1	Demographics tables will be generated for 5 analysis sets: ITT, mITT, Safety, PK, and Completers. Added variables rate pressure product (bpm*mmHg), Beta-hydroxybutyrate (mmol/L). Removed ratios of LDL-C/LDL-C. Added unit (%) for HbA 1c . A minor correction for baseline HbA 1c categories was made.
4.2	Screen failures will not be summarized. Protocol deviations will be listed that may include deviations related to medication dispensed. Removed the bullet of “reasons for discontinuation from study” as it is redundant with the paragraph below.
4.3	Treatment compliance formula was refined to only account for period of time between first and last dose; non-compliance is not counted after the last dose.
4.2, 4.3	Changed “study agent” to “treatment” to keep the consistency through the SAP.
4.4	For the purpose of summarizing exposure, treatment duration does not take drug interruptions into account. Steps for imputing missing treatment end dates were refined. Removed “study agent” from the second paragraph of the section. Replaced “treatment duration prior to rescue medication” and “treatment duration” for “treatment duration” and “overall duration”, respectively.
4.5	Protocol deviations, as identified by the Study Team, will be listed but not summarized.
5.0, 5.2.3, 5.4.2	“Data collected after the last dose plus 7 days” changed to “Data collected after the last dose plus 14 days will be excluded from the mITT analysis.” This change is based on what is known about PK.
5.1.1	Clarify adjusted p-values will be presented comparing each JNJ-64565111 dose to placebo in the summary tables.
5.2.3, 5.4.2	For endpoints with only one post-baseline visit, an ANCOVA model will be used with treatment as a fixed factor and baseline as a covariate.
5.2.3	Change “Sensitivity Analysis” to “Supportive Analysis”.
5.2.3	Change the minimum number of subjects from 80 to 40 as the threshold to perform subgroup analyses. Clarified 2- and 3-way interaction terms with treatment will be included in the model.
5.2.3, 5.3.2	Allow for copy control method to be used if there are not enough retrieved drop-outs to impute missing data as originally intended.
1.3, 5.3.1, 5.4.1	Reworded the efficacy endpoints to reduced awkwardness of phrasing (e.g., “absolute change from baseline in body weight” from “absolute change in body weight from baseline”).
5.3.2, 5.4.2	The analysis of categorical endpoints will be performed using logistic regression given the challenges of running a longitudinal categorical analysis in which few subjects at the early time points are considered responders.
5.4.2	Added lists of endpoints for MMRM and ANCOVA analyses. Added shift table for obesity class.
5	All efficacy analyses for non-glycemic endpoints will be performed regardless of rescue medication. Analyses of glycemic endpoints (i.e., HbA 1c , FPG, fasting insulin, HOMA-B, HOMA-IR) will accordingly be based on a prior to rescue medication analysis.

SECTION(S)	CHANGE and RATIONALE
6	Reference to Section 2.3.4 should be 2.2.3.
6.1	Mild and Moderate AEs will not be pooled for the purpose of summarizing AEs by severity.
6.2, 6.3	References to Attachments 4 and 5 should be Attachments 1 and 2, respectively.
6.2	Shift tables for laboratory values will not be generated.
6.2	“Markedly abnormal” laboratory values are not defined.
7.1	The details under which measurements should be excluded from the PK analysis are provided.
References	Added references 4 and 5 for IWQOL-Lite.
ATCH 2	Added PDLCs for calcitonin, amylase and lipase.
ATCH 2	Beta-Hydroxybutyrate above 20.822 mg/dL will be flagged as PDLC.
ATCH 3	Refer to Excel files; reference in ERIS.

**ABBREVIATIONS**

β-hCG	Serum β-human chorionic gonadotropin
ADA	anti-drug antibody
AE(s)	Adverse event(s)
AHA	Antihyperglycemic agent
ANCOVA	Analysis of Covariance
ATC	Anatomical Therapeutic Chemical
BMI	Body mass index
bpm	Beats per minute
CI	Confidence interval
CKD-Epi	Chronic Kidney Disease Epidemiology Collaboration
DBP	Diastolic blood pressure
DMC	Data Monitoring Committee
eCRF(s)	Electronic case report form(s)
eGFR	Estimated glomerular filtration rate
EOT	End-of-treatment
ERCQ	Eating-related Concept Questionnaire
FPG	Fasting plasma glucose
GCP	Good Clinical Practice
GLP-1	Glucagon-like peptide-1
HbA 1c	Hemoglobin A 1c
HDL-C	High-density lipoprotein cholesterol
HOMA-B	Homeostasis Model Assessment for B cell function
HOMA-IR	Homeostasis Model Assessment of insulin resistance
IA	Interim analysis
ITT	Intent-to-treat
IWQOL-Lite	Impact of Weight on Quality of Life-Lite
IWRS	Interactive web response system
LDL-C	Low-density lipoprotein cholesterol
MACE	Major adverse cardiovascular events
MedDRA	Medical Dictionary for Regulatory Activities
mITT	Modified intent-to-treat
mmHg	Millimeters mercury
MMRM	Mixed model for repeated measures
PK	Pharmacokinetics
PRO	Patient-reported outcome (paper or electronic as appropriate for this study)
PROMIS SF 10a	PROMIS physical function Short Form 10a
SAE(s)	Serious adverse event(s)
SAP	Statistical analysis plan
SBP	Systolic blood pressure
SC	Subcutaneous, subcutaneously
SD	Standard deviation
SI	International System of Units
T2DM	Type 2 diabetes mellitus
TEAE(s)	Treatment-emergent adverse event(s)
ULN	Upper limit of normal
WHO	World Health Organization

## 1. INTRODUCTION

This statistical analysis plan (SAP) contains the definitions of analysis sets, key derived variables, and statistical methods for the analyses of efficacy and safety data from study JNJ-64565111OBE2002. This SAP is based on the Clinical Protocol JNJ-64565111OBE2002 dated 5 April 2018. Titles, mock-ups and programming instructions for all statistical outputs (tables, figures and listings) will be provided in a separate document entitled Data Presentation Specifications (DPS). A separate Data Monitoring Committee (DMC) SAP will describe the data analysis for DMC reviews.

### 1.1. Trial Objectives

#### Primary Objectives

The primary objectives are to assess the effects of JNJ-64565111 compared with placebo in severely obese subjects with Type 2 Diabetes Mellitus (T2DM) after 12 weeks of treatment on:

- the percentage change from baseline in body weight
- safety and tolerability

#### Secondary Objectives

The secondary objectives are to assess the effects of JNJ-64565111 compared with placebo in severely obese T2DM subjects after 12 weeks of treatment on:

- the absolute change from baseline in body weight
- the proportion of subjects with  $\geq 5\%$  weight loss from baseline

#### Exploratory Objectives

The exploratory objectives are to assess the effects of JNJ-64565111 compared with placebo in severely obese T2DM subjects after 12 weeks of treatment on:

- the proportion of subjects with  $\geq 10\%$  weight loss from baseline
- the change from baseline in body mass index (BMI)
- the change from baseline in waist circumference
- the change from baseline in glycated hemoglobin (HbA1c)
- the change from baseline in fasting plasma glucose (FPG)
- the change from baseline in fasting insulin
- the change from baseline in fasting C-peptide
- the changes from baseline in Homeostasis Model Assessment for B cell function (HOMA-B) and HOMA-insulin resistance (IR)
- the change from baseline in systolic blood pressure (SBP)
- the change from baseline in diastolic blood pressure (DBP)

- the change from baseline in pulse rate
- the change from baseline in rate pressure product
- the change from baseline in fasting lipids (total cholesterol, low-density lipoprotein cholesterol [LDL-C], high-density lipoprotein cholesterol [HDL-C], and triglycerides)
- pharmacokinetic (PK) exposure
- the change from baseline in scores on the Impact of Weight on Quality of Life – Lite (IWQOL-Lite)
- the change from baseline in scores on the Patient-Reported Outcomes (PRO) Measurement Information System (PROMIS®) Physical Function Short Form 10a (PROMIS SF 10a)
- the change from baseline in scores on the Eating-related Concept Questionnaire (ERCQ)

## 1.2. Trial Design

This is a randomized, double-blind, placebo-controlled, parallel-group, 4-arm, multicenter study in severely obese subjects with T2DM. Subjects who are  $\geq 18$  and  $\leq 70$  years of age and have a BMI  $\geq 35$  kg/m^2 to  $\leq 50$  kg/m^2 are eligible to participate if they have a HbA1c of  $\geq 6.5\%$  to  $\leq 9.5\%$  at the screening visit on diet and exercise alone or on a stable dose of single oral antihyperglycemic agent (AHA) or dual-combination oral AHAs for  $\geq 12$  weeks prior to screening. A target of 188 subjects will be randomly assigned in this study.

Subjects meeting all enrollment criteria will enter a 2-week run-in phase, which is to occur approximately 1 week after the screening visit and is designed to train the subject on SC self-injection and to establish the subject's ability to comply with the protocol-specified requirements. On Day 1 (date of first dose), subjects who continue to meet eligibility criteria, will be randomly assigned in a 1:1:1:1 ratio to blinded treatment with placebo or JNJ-64565111 5.0 mg, 7.4 mg, or 10 mg and enter a 12-week treatment phase. Post-randomization visits will be conducted at Week 2, 6, 12/end-of-treatment [EOT] visit, and the SAE follow-up visit 5 weeks after the last dose of study drug. At Weeks 4 and 10, all subjects will be contacted preferably by telephone to reinforce the adherence to diet and exercise, study drug dosing reminder, assessment of subjects' status, and compliance with the protocol procedures (eg, diary completion reminder).

Subjects who withdraw from the study will not be replaced.

During the 12-week treatment phase (Day 1 to Week 12), subjects meeting protocol-specified glycemic rescue criteria will have rescue therapy initiated, and will remain in the study, continuing double-blind study drug. Rescue therapy may include increasing the dose of a current AHA or the initiation of a new AHA. Investigators will manage rescue therapy, including the selection of the specific AHA, its clinically appropriate initial dose and titration regimen (if applicable), the need to switch from one AHA rescue medication to another (ie, poor glycemic response to prior rescue medication), and be consistent with the labeled use within the country of the study site. Metformin, sulphonylureas, thiazolidinediones (TZDs), sodium-glucose cotransporter 2 (SGLT-2) inhibitors, dipeptidyl peptidase-4 (DPP-4) inhibitors, and insulin (basal

only) are allowed as rescue medication; GLP-1 agonists and short-acting or intermediate insulins are not allowed as rescue medication.

The overall study duration is approximately 19 weeks and comprises of 3 phases:

[figure not shown]
- Pretreatment phase: 3 weeks comprised of:
  - Screening phase: 1 week
  - Run-in (injection-training) phase: 2 weeks
- Treatment phase (double-blind)
  - Placebo-controlled treatment phase: 12 weeks
- Post-treatment phase (SAE follow-up visit): 4 weeks

A diagram of the study design is provided in [Figure 1.2.1](#).

**Figure 1.2.1: Schematic Overview of the Study**

#### Screening

- Age  $\geq 18$  to  $\leq 70$  years
- BMI  $\geq 35$  to  $\leq 50$  kg/m^2
- HbA1c  $\geq 6.5\%$  to  $\leq 9.5\%$
- On diet/exercise alone, or on stable dose of single oral AHA, or dual oral combination AHAs for  $\geq 12$  weeks

### 1.3. Statistical Hypotheses for Trial Objectives

In severely obese T2DM subjects, at least one dose JNJ-64565111 compared with placebo at 12 weeks leads to a greater:

#### Primary:

- percentage reduction from baseline in body weight

**Secondary:**

- absolute reduction from baseline in body weight
- proportion of subjects with  $\geq 5\%$  weight loss from baseline

**1.4. Sample Size Justification**

A total of 188 subjects will be randomly assigned in this study with 47 subjects per group allocated to each of the 4 treatment groups. Sample size was determined based on assessing the primary hypothesis that at least one dose of JNJ-64565111 leads to greater percentage reduction in body weight at 12 weeks compared with placebo.

Assuming a common SD of 4% with respect to percent change in body weight at Week 12 and a 2-sided type I family-wise error rate of 0.05, it is estimated that a sample size of 47 randomly assigned subjects per group will have approximately 90% power to detect a treatment difference of 2.7%.

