9.2. Sample Size Determination

A total of 188 subjects will be randomly assigned in this study with 47 subjects per group allocated to each of the 4 treatment groups. Sample size was determined based on assessing the primary hypothesis that treatment with JNJ-64565111 at 1 or more dose levels for 12 weeks leads to greater percentage reduction in body weight compared with placebo.

Assuming a common SD of 4% with respect to percent change in body weight at Week 12 and a 2-sided type I error rate of 0.05, it is estimated that a sample size of 47 randomly assigned subjects per group will have approximately 90% power to detect a treatment difference of 2.7%.

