### **5.1. Analysis Specifications**

#### **5.1.1. Level of Significance**

The type I error rate will be strongly controlled at  $\alpha=5\%$  for each of the primary endpoint and secondary endpoints. The Hochberg approach will be used to adjust for the multiplicity of the comparisons of each of the JNJ-64565111 doses versus placebo for each of the primary and major secondary efficacy endpoints. Adjusted p-values will be provided.

Unless otherwise specified, all statistical tests will be interpreted at a 2-sided significance level of 5% and all confidence intervals at a 2-sided confidence level of 95%. Nominal p-values will be presented for endpoints other than those described above.

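### SAP 1.4 claims about 90% power at a family-wise 0.05, but that is the unadjusted one-comparison figure; under the planned Hochberg test it is about 80% if only one dose has the 2.7% effect

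*SAP*

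**What the plan says.** SAP 1.4 sets the size of the trial: "A total of 188 subjects will be randomly assigned in this study with 47 subjects per group allocated to each of the 4 treatment groups". The inputs are "Assuming a common SD of 4% with respect to percent change in body weight at Week 12", a difference of 2.7% from placebo, about 90% power, and a "2-sided type I family-wise error rate of 0.05, it is estimated that a sample size of 47 randomly assigned subjects per group". The hypothesis being powered is the "primary hypothesis that at least one dose of JNJ-64565111 leads to greater percentage reduction in body weight at 12 weeks compared with placebo".

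Protocol 9.2 has the same sample size, SD, difference and power, and says that the design "will have approximately 90% power to detect a treatment difference of 2.7"%. It describes the error rate only as "a 2-sided type I error rate of 0.05, it is estimated that a sample size of 47 randomly assigned subjects per group", with no mention of a family.

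There are three active arms, with subjects "randomly assigned in a 1:1:1:1 ratio to blinded treatment with placebo or JNJ-64565111 5.0 mg, 7.4 mg, or 10 mg". SAP 5.1.1 controls the family: "The Hochberg approach will be used to adjust for the multiplicity of the comparisons of each of the JNJ-64565111 doses versus placebo". Protocol 9.4.1 plans the same procedure.

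Neither sample-size section says how many doses are assumed to have the 2.7% effect. Neither says whether power means a given dose, any dose or all doses, and neither allows for missing Week 12 weights.

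**The concern.** Between the protocol and the SAP the error rate changed from an ordinary type I rate to a family-wise one, and no other number changed. With three comparisons and a multiplicity procedure, the power for a given comparison cannot stay the same. Either the 90% was calculated without the adjustment, or it refers to some other definition of power that is not stated.

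This matters because the study is meant to choose Phase 3 doses (Protocol 2.1 and 4.2.1). A reader of SAP 1.4 would conclude that a dose with a true 2.7% effect has about a 10% chance of missing significance after multiplicity control. If only one dose has that effect, the chance is about 19%, roughly double. A non-significant dose could then be read as stronger evidence against that dose than it is.

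**Working it through.** **Inputs.** n = 47 per arm, SD 4, difference 2.7, two-sided 0.05 (SAP 1.4); three doses against a shared placebo arm, 1:1:1:1 (SAP 1.2); Hochberg (SAP 5.1.1).

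**1. Reproduce the plan's figure.** For one comparison at unadjusted alpha, the normal formula is

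n = 2 × (SD/difference)² × (z₀.₉₇₅ + z₀.₉₀)² = 2 × (4/2.7)² × (1.960 + 1.282)² = 46.1, rounded up to 47.

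This is exactly the plan's sample size. For the t-test, the noncentrality is 2.7 / (4 × √(2/47)) = 3.272 and the critical value on 92 df is 1.986, which gives **89.9%** power. The stated figure therefore reproduces as a single unadjusted comparison in which all 47 subjects per arm are analysed.

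**2. Other readings of the error rate.**

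| Test of one dose, n = 47 | Power |
|---|---|
| Unadjusted 0.05 (t) | 89.9% |
| 0.025 (t) | 83.8% |
| 0.05/3 = 0.0167, Bonferroni (t) | 79.6% |
| Dunnett single-step, critical value 2.35 | 82.2% |

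None of the adjusted versions gives 90% for a given dose. At 0.0167 (Bonferroni, a reference point and not the planned test) the difference detectable with 90% power is 3.08%.

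**3. The planned procedure.** Hochberg orders the three p-values. If the largest is at or below 0.05, all three are rejected. If not, and the middle one is at or below 0.025, the two smaller are rejected. If not, the smallest is compared with 0.0167. It was simulated with a shared placebo arm, pooled-variance t-tests and at least 300,000 replicates per scenario. The rate of any rejection when no dose works was about 4.5%. Results at n = 47 with complete data:

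| True effects (%) | A dose with the 2.7% effect | At least one effective dose | All effective doses |
|---|---|---|---|
| 0 / 0 / 2.7 | 80.6% | 80.6% | 80.6% |
| 0.9 / 1.8 / 2.7 | 81.6% (top dose) | 83.6% | 16.1% |
| 0 / 2.7 / 2.7 | 83.5% | 91.7% | 75.2% |
| 2.7 / 2.7 / 2.7 | 87.8% | 95.5% | 78.7% |

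In the one-dose case the miss risk is 100 − 80.6 = 19.4%, against about 10% as stated. Reaching 90% in that case would take about 60 per arm (simulated 90.3%), or 240 in total.

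**4. Missing Week 12 weights.** The documents give no rate, so 10% and 20% are assumptions. 47 × 0.90 = 42.3 and 47 × 0.80 = 37.6, taken as 42 and 38 per arm. Missing subjects are treated as lost sample.

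| n per arm | Unadjusted, one comparison (t) | Hochberg, one effective dose | Hochberg, at least one of two | Hochberg, at least one of three |
|---|---|---|---|---|
| 47 | 89.9% | 80.6% | 91.7% | 95.5% |
| 42 | 86.4% | 75.1% | 88.3% | 93.1% |
| 38 | 82.7% | 70.1% | 84.5% | 90.4% |

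**The case against.** The strongest reply is that the hypothesis concerns at least one dose and does not suppose that two of the three are inert. The sponsor had reason to expect more. Protocol 4.3 anticipates clinically meaningful weight loss at 7.4 and 10 mg. The Phase 1 results in Protocol 2.2 show 4-week losses of 3.0%, 4.1% and 3.9% at the weight-based equivalents of 5, 7.4 and 10 mg, with no change on placebo. In the fixed-dose study the losses were about 4% at 5 and 10 mg against about 1% on placebo. If two or three doses have the 2.7% effect, the at-least-one-dose power is 91.7% or 95.5%, and about 90% at a family-wise 0.05 is then a fair description.

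That arithmetic is right, and it means the trial is not underpowered in every scenario. It does not rescue the sentence in SAP 1.4, which names neither the scenario nor the definition of power on which the reply depends. The match at n = 47 points instead to a one-comparison calculation. No formula is given, so this attribution is an inference. For any named dose, which is what dose selection turns on, power stays below 90% in every scenario examined.

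A second reply is that treating missing subjects as deleted is pessimistic. The mixed model uses the Week 2 and Week 6 weights, adjusts for baseline weight, and keeps weights up to 14 days after the last dose. The Week 12 window (Days 65 to 105) is also wide. This stands in part: some precision would be recovered. The documents give no correlations from which to say how much, and SAP 1.4 claims no such gain.

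It is also true that planned power does not enter the analysis. Type I error control, the estimates and the confidence intervals are unaffected.

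**Conclusion.** The concern holds: the power statement in SAP 1.4 is wrong as written. The 90% is what one unadjusted comparison gives with complete data (89.9%), and it is presented as power at a family-wise 0.05. Under Hochberg at 47 per arm, power for a dose with a true 2.7% effect is about 80.6% if it is the only effective dose, 83.5% if two are effective and 87.8% if all three are. The 90% is met only as at-least-one-dose power with two or three effective doses, which the SAP does not state.

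These figures rest on the plan's own SD and difference, equal arms, normal outcomes and complete data. The lower figures of about 75% and 70% rest also on assumed losses of 10% and 20%, with no allowance for what the mixed model might recover. The conclusion concerns the stated power and how a non-significant dose would be read; the validity of the tests is not in question.

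**What to change.** Restate SAP 1.4 and leave the sample size as it is:

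- Say that 47 per group gives about 90% power for one dose-placebo comparison at an unadjusted two-sided 0.05 with complete Week 12 data.
- Give power under Hochberg at a family-wise 0.05, naming the definition each time: about 80% if only one dose has a 2.7% effect; about 84% per dose and 92% for at least one effective dose if two do; about 88% per dose and 96% for at least one if all three do.
- Say which of these scenarios the sponsor regards as the planning case, and why.
- Add the same figures for a stated range of missing on-treatment Week 12 weights, for example 10% to 20%, marked as an assumption.

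In Protocol 9.2, one added clause saying that the error rate is per comparison would bring the two documents into line.

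The cost is wording only: no extra subjects and no change to the tests. The stated power becomes less favourable.

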**1.5. Randomization and Blinding**

On Day 1, subjects will be randomly assigned to 1 of 4 treatment groups based on a computer-generated randomization schedule prepared before the study by or under the supervision of the sponsor. The randomization will use randomly permuted blocks.

At baseline (Day 1), the treatment code, which is linked to the randomization schedule, will be assigned after logging on to the IWRS designated by the sponsor. The requestor must use his or her own user identification and personal identification number when contacting the IWRS, and will then give the relevant subject details to uniquely identify the subject. Based on this information, the IWRS will assign a unique treatment code, which will dictate the treatment assignment and matching study drug kit for the subject. As subjects are randomly assigned to treatment, the IWRS will assign a study drug kit to be dispensed at that visit. New study drug kits will be assigned each time the IWRS is accessed for dispensing additional study drug.

